#### SECONDARY HYPOTHESES

3. A blood pool contrast agent such as gadofosveset trisodium has better precision and accuracy in discriminating different degrees of liver fibrosis, compared to extra-cellular gadolinium agents such as Gd-BOPT.
4. Arterial spin labeling (ASL) can provide perfusion metrics used to discriminate different degrees of liver fibrosis.
5. There is a change in portal flow, hepatic perfusion fraction measured with IVIM DW-MRI and in hepatic/splenic stiffness measured with MRE from fasting to non fasting state.

 Mount Sinai	Protocol Title:	Detection of Liver Fibrosis Using IVIM Diffusion and DCE MRI in HCV
	Principal Investigator Name/Contact Info:	[name]
	Primary Contact Name/Contact Info	[name] [contact] [contact]
	Date Revised:	9/16/2016
	Study Number:	GCO09-1187

## 2) Background

There is an expected increased incidence of chronic hepatitis C virus infection (HCV) in the United States within the next years, with subsequent increased risks of liver damage, including fibrosis and cirrhosis, which may eventually lead to hepatocellular carcinoma and end-stage liver disease requiring liver transplantation. This disease is/will be the source of enormous health care costs and morbidity/mortality. Most hepatologists still rely on liver biopsy findings in patients newly diagnosed with HCV, which enables the assessment of liver damage (fibrosis and inflammation). Liver biopsy has limitations, including cost, invasiveness, poor patient acceptance, limited sampling, inter-observer variability and is difficult to repeat. Non invasive tests to capture the extent of liver damage at a larger scale are urgently needed. These will gain more acceptance among patients and hepatologists. In this proposal, we would like to test and validate non invasive magnetic resonance imaging (MRI) methods based on advanced diffusion (intravoxel incoherent motion diffusion MRI: IVIM DW-MRI) and dynamic contrast-enhanced MRI (DCE-MRI) for the detection of fibrosis and cirrhosis in HCV patients. Based on our recent preliminary data, we believe that the combination of IVIM DW- and DCE-MRI has potential for detection of fibrosis and cirrhosis with excellent accuracy, while enabling coverage of the whole liver. In order to improve the diagnostic performance of MRI, we would like to build and validate a predictive model based on advanced functional MRI metrics (diffusion and perfusion). If validated, this novel non invasive algorithm will not only decreases the number of liver biopsies, but also enable earlier diagnosis of liver fibrosis when antiviral treatment is more effective, and enable a comprehensive evaluation of the liver (to assess for cirrhosis, portal hypertension and hepatocellular cancer). This could significantly reduce the cost of care, could become a useful tool for testing new antifibrogenic and antiviral drugs in HCV, and could be used to follow patients for detection of progression to cirrhosis. This will be a highly significant progress in liver diseases given the increased burden of HCV in this country, and would benefit a large number of Americans over the next decade.

Purpose of study:

- 1) Determine the prospective diagnostic performance of DW-MRI, DCE-MRI and MRE for staging liver fibrosis in patients with chronic liver disease in comparison to controls.
- 2) Compare the diagnostic performance of MRI vs. transient elastography (TE) and acoustic radiation force impulse (ARFI) imaging and serum markers for non invasive detection of liver fibrosis in patients with chronic liver disease in comparison to controls.

Secondary Objectives:

- 1) Assess the role of a breath-hold/free-breathing phase contrast MR imaging sequence to assess portal vein and hepatic artery velocity and flow.
- 2) Assess the role of hepatic and splenic stiffness measured with MRE as surrogate measures of portal hypertension (measured with portal pressures, which will be clinically indicated).

 Mount Sinai	Protocol Title:	Detection of Liver Fibrosis Using IVIM Diffusion and DCE MRI in HCV
	Principal Investigator Name/Contact Info:	[name]
	Primary Contact Name/Contact Info	[name] [contact] [contact]
	Date Revised:	9/16/2016
	Study Number:	GCO09-1187

- 3) Assess the role of a FDA approved blood pool gadolinium contrast agent, Gadoxedate disodium (Eovist), Lantheus) for the measurement of liver MR Perfusion, compared to extra-cellular contrast agents.
- 4) Assess the role of arterial spin labeling (a non contrast technique) for measurement of hepatic perfusion.

### **3) Setting of the Human Research**

Mount Sinai Medical Center - Department of Radiology/Translational and Molecular Imaging Institute (TMII)

### **4) Resources Available to Conduct the Human Research**

We have the equipment (MRI scanners, Fibroscan and ARFI) and we are in an open dialogue with the staff of Liver disease and liver transplant to be able to recruit the subjects needed to complete this study.

### **5) Study Design**

#### **a) Recruitment Methods**

Subjects with liver disease will be identified and recruited for the study by their physicians in the Liver Transplant and/or Liver Disease team. This selection will come from the physicians' recommendation, which is familiar with their patient's history. The referring physicians will not be considered co-investigators except [name] and [name]. [name] and [name] are both Co-investigators on this project. They will tell the other physicians in Liver Transplant and Liver Disease about the study and help to enroll patients.

Other sources of potential subjects are the KCC ambulatory procedure list and the Mount Sinai Liver Transplant list provided by the Liver Transplant/Liver Disease Department. Subjects with liver disease who underwent liver biopsy at Mount Sinai will be identified by [name] from the Pathology Department. [name] is a Co-investigator on this study and provides the study team with a quarterly Pathology list.

The treating physician will be the first to notify potential subjects about the study. If subjects consent to be contacted the Research Coordinator will call them to explain the study and to ask if they are willing to be part of this study. No potential subject will be contacted by the study team without subject's prior consent. The study coordinator will review all listings and the patient's medical records to check for their eligibility according to the inclusion/exclusion criteria and contraindications for MRI. A HIPAA waiver of authorization will be requested for the study.

An announcement within the MSSM Broadcast emails will be used for recruitment.

 Mount Sinai	Protocol Title:	Detection of Liver Fibrosis Using IVIM Diffusion and DCE MRI in HCV
	Principal Investigator Name/Contact Info:	[name]
	Primary Contact Name/Contact Info	[name] [contact] [contact]
	Date Revised:	9/16/2016
	Study Number:	GCO09-1187

*ResearchMatch will also be used as a method for identifying and contacting potential subjects. The study specific announcement is included with this submission.*

## **b) Inclusion and Exclusion Criteria**

### **Inclusion criteria**

Study group

- 1) Chronic liver disease (including viral hepatitis, alcoholic hepatitis, non alcoholic steatohepatitis, primary biliary cirrhosis, primary sclerosing cholangitis, etc.)
- 2) 18 years of age and older
- 3) Patient is able to give informed consent for this study and agrees to provide a blood sample  
Patients preferably (but not necessarily) underwent/will undergo:
- 4) Liver biopsy (percutaneous or transjugular or surgical) performed within 6 months, as part of routine clinical care and/or
- 5) Liver transplant or liver resection performed as part of routine clinical care and/or
- 6) Medical therapy for portal hypertension or TIPS placement as part of routine clinical care and/or

Antiviral therapy for HCV infection.

Control group

- 1) Patients without history of liver disease and healthy volunteers
- 2) 18 years of age and older
- 3) Subject is able to give informed consent for this study and agrees to provide a blood sample

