## Brief Summary of Research (250-400 words):

### 1) Objectives:

#### *Research Question:*

#### MAIN HYPOTHESES

1. IVIM, DCE-MRI and MRE metrics can non invasively discriminate severe fibrosis/cirrhosis (F3-F4), from no fibrosis (F0) and intermediate fibrosis (F1-F2). To test our hypothesis, we will prospectively determine in a cohort of 100 subjects (including 80 with chronic liver disease and 20 controls) whether IVIM DW-MRI, DCE-MRI and MRE parameters are valid markers of liver fibrosis, using histopathology from liver biopsy or explant as the reference.
2. MRI has equivalent performance to ultrasound elastography [including TE (transient elastography, Fibroscan) and ARFI (Acoustic Radiation Force Impulse imaging, Siemens) and serum markers for staging liver fibrosis, with the advantage of being more comprehensive and by providing whole liver coverage.

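### Nothing in the plan balances or adjusts for age or sex between controls and liver patients, so contrasts that use controls can partly reflect age or sex

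*Combined protocol and SAP*

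**What the plan says.** **Role of controls.** Main Hypothesis 1 plans a cohort of "100 subjects (including 80 with chronic liver disease and 20 controls") and asks whether the MRI metrics separate F3-F4 from F0 and from F1-F2. Purpose 1, in section 2, is to determine diagnostic performance "for staging liver fibrosis in patients with chronic liver disease in comparison to controls". Purpose 2 sets the comparison of MRI with TE, ARFI and serum markers against controls in the same way.

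**Who may be a control.** Section 5(b) admits "Patients without history of liver disease and healthy volunteers". The other two conditions are "18 years of age and older", which applies equally to the study group, and consent with a blood sample. There is no upper age limit, age band, sex quota or matching rule.

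**Where subjects come from.** Section 5(a) says: "Subjects with liver disease will be identified and recruited for the study by their physicians in the Liver Transplant and/or Liver Disease team". It adds a procedure list, the transplant list and a quarterly pathology list. Two further routes are named without being assigned to either group: "An announcement within the MSSM Broadcast emails will be used for recruitment", and "ResearchMatch will also be used as a method for identifying and contacting potential subjects".

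**Analysis.** The protocol has no statistical analysis section. Section 5(e) gives the endpoint as fibrosis detection and staging, with no model or covariates. Section 5(c) gives 250 subjects, without a split into patients and controls.

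**The concern.** The two groups are defined differently and, for the most part, found differently. Patients are people under the care of liver or transplant physicians. Controls are any adults without known liver disease, and the only listed routes not tied to liver services or clinical lists are the broadcast email and ResearchMatch. Nothing in this arrangement makes the groups alike in age or sex, and nothing in the analysis allows for a difference.

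If a perfusion, diffusion or stiffness metric varies with age or sex, part of any gap between patients and controls belongs to those factors and not to fibrosis. The apparent AUC against controls is then biased, usually upwards when the age effect and the fibrosis effect run in the same direction. A comparison between tests (MRI against TE, ARFI or serum markers) is also distorted if the tests differ in how strongly they depend on age or sex.

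This is separate from how severe the patients' disease is. It would remain if every patient in the comparison had mild fibrosis.

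**Working it through.** The documents state no alpha, effect size, age distribution or age effect, so there is no planned figure to reproduce. The check is in two parts.

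**1. Which contrasts involve controls**

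| Contrast | Source | Uses controls? |
|---|---|---|
| Patients versus controls | Section 2, Purposes 1 and 2 | Yes |
| F3-F4 versus F0 | Main Hypothesis 1 | So far as controls supply F0 |
| F3-F4 versus a pooled F0-F2 group | One reading of Main Hypothesis 1 | Partly |
| F3-F4 versus F1-F2 among patients | Main Hypothesis 1 | No |

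**2. How large the effect could be**

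From the document: 80 patients and 20 controls (Main Hypothesis 1). Assumed, and not in the documents: mean age gap of 10 to 20 years, metric slope of 0.01 to 0.03 SD per year, no effect of fibrosis on the metric, normal distributions with equal SD, and a two-sided 5% t test.

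- Spurious standardised difference: d = slope × age gap.
- AUC = Φ(d/√2).
- Rejection rate: noncentral t with 98 degrees of freedom and noncentrality d × √(80 × 20/100) = 4d.

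| Slope × gap | d | d/√2 | AUC | Noncentrality | Rejection rate |
|---|---|---|---|---|---|
| 0.01 × 10 | 0.10 | 0.071 | 0.528 | 0.4 | 6.8% |
| 0.02 × 20 | 0.40 | 0.283 | 0.611 | 1.6 | 35.4% |
| 0.03 × 20 | 0.60 | 0.424 | 0.664 | 2.4 | 66% |

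*Other assumptions.* Suppose the metric has correlation 0.1 to 0.5 with age and the groups differ by 0.5 to 1.5 SD of age. Then d = correlation × gap runs from 0.1 × 0.5 = 0.05 to 0.5 × 1.5 = 0.75. The AUC runs from 0.51 to 0.70, and the chance of a significant result (upper tail only) from about 4% to 85%. The range again starts close to no effect.

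*Pooled comparison.* Suppose 40 F3-F4 patients are compared with 40 F1-F2 patients plus 20 controls, with no age difference among patients. This split is an assumption. Two thirds of the comparison group then contribute an AUC of 0.50 and one third the value above:

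- (2/3)(0.50) + (1/3)(0.528) = 0.51
- (2/3)(0.50) + (1/3)(0.611) = 0.54
- (2/3)(0.50) + (1/3)(0.664) = 0.55

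*More subjects.* If the 250 of section 5(c) kept the 4:1 ratio (assumed: 200 and 50), the AUCs would not change, and the rejection rates would rise to 9.7%, 71.2% and 96.6%. A larger sample does not reduce this bias; it makes it easier to declare significant.

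Sex works the same way, with d equal to the difference in the proportion of men multiplied by the male-female difference in SD. The documents give neither term, and no figure is offered for it.

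**The case against.** The case on the other side is substantial, and much of it limits the point.

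- **Recruitment routes.** A reader might infer that controls are recruited by staff email and ResearchMatch and so must be younger than the patients. Section 5(a) does not say this. Neither route is assigned to controls, the text does not describe the email as going to staff, and both routes could bring in patients. Section 5(b) also admits patients without liver disease, who may resemble the liver patients in age. A systematic age gap is possible but not established.
- **Reach.** A reader might take all the fibrosis results to be affected. They are not: F3-F4 versus F1-F2 among patients involves no controls, and a pooled comparison dilutes the effect. The direct test of 80 against 20 is an illustration, since the documents specify no such test. The two Purposes still make controls a comparator.
- **Assumed size.** Age gap and slope are both assumed, and the low end is close to the nominal 5%. This is correct. The figures show what could happen, not what will.
- **Chance imbalance.** A reader might say that with 20 controls any imbalance is indistinguishable from disease. That goes too far. Chance imbalance is already covered by the nominal error rate, and measured age and sex can be adjusted for where the groups overlap. The problem is systematic imbalance left unadjusted.
- **A wider gap.** With no analysis section, no covariate of any kind is addressed. That is true, but control selection is a design choice that is hard to repair later: if the age ranges barely overlap, adjustment cannot replace matching.

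It might also be said that controls serve only for image optimisation. Section 5(b) gives that reason only for giving gadolinium to healthy volunteers, not for having controls.

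**Conclusion.** The point holds for contrasts that use controls: the patient-control comparisons in both Purposes, and F3-F4 versus F0 so far as controls supply F0. The plan as written has no safeguard against age or sex confounding there, in design or in analysis. It does not hold for F3-F4 versus F1-F2 among patients.

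The size is unknown. The illustrated range for a direct comparison runs from negligible to material, and it rests wholly on the assumed gaps and slopes and on 80 and 20 being the numbers analysed. That split is itself unsettled, because section 5(c) gives 250 without one. The documents do not show that the groups will differ in age or sex, only that nothing prevents or corrects it. The change is worth making because it is cheap and has most value before controls are enrolled.

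**What to change.** 1. In section 5(b), frequency-match controls, however many are enrolled, to the patients on sex and broad age band.
2. In section 5(h), state that age in years and sex are kept in the coded research data. It should not be assumed that they already are: the protocol treats date of birth as an identifier to be stored apart from the research data, and it nowhere lists sex as a recorded variable.
3. For every contrast that uses controls, report an age- and sex-adjusted result (for example a covariate-adjusted ROC curve) next to the unadjusted one, with the age and sex distribution of each group.
4. For the staging contrast, also report a patient-only result.

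The cost is somewhat slower filling of control places, two recorded variables and slightly more analysis. No extra subjects, scans or procedures are needed. If some controls are already enrolled, items 2 to 4 still apply, and matching can steer the remaining places.

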### **Exclusion criteria**

1. Age less than 18 years
2. Unable or unwilling to give informed consent
3. Contra-indications to MRI
  - a. Electrical implants such as cardiac pacemakers or perfusion pumps
  - b. Ferromagnetic implants such as aneurysm clips, surgical clips, prostheses, artificial hearts, valves with steel parts, metal fragments, shrapnel, tattoos near the eye, or steel implants
  - c. Ferromagnetic objects such as jewelry or metal clips in clothing
  - d. Pregnant subjects
  - e. Pre-existing medical conditions including a likelihood of developing seizures or claustrophobic reactions.

As with all subjects referred for MRI, each subject is screened for possible contraindications with a routine questionnaire.

Subjects with GFR <30 will not undergo DCE-MRI with Gadolinium contrast. For subjects with GFR <30, we will still consider enrolling them for a non-contrast MR protocol, including non-contrast sequences, FibroScan and/or ARFI and blood tests. Subjects with GFR between 30 and

	Protocol Title:	Detection of Liver Fibrosis Using IVIM Diffusion and DCE MRI in HCV
	Principal Investigator Name/Contact Info:	[name]
	Primary Contact Name/Contact Info	[name] [contact] [contact]
	Date Revised:	9/16/2016
	Study Number:	GCO09-1187

60 will receive only either a half dose Multihance or Gadoxedate disodium (Eovist), and will not have repeat DCE-MRI studies with Gadolinium contrast. Only subjects with GFR  $\geq 60$  will be proposed to return for repeat DCE-MRI studies with Gadolinium contrast. Subjects with GFR  $< 60$  will be considered to return for repeat non-contrast MRI-studies.

We will consider injecting gadolinium contrast in healthy volunteers, for the purpose of DCE-MRI image optimization.

### c) Number of Subjects

250

### d) Study Timelines

6 years

### e) Study Endpoints

Liver fibrosis detection and staging

### f) Procedures Involved in the Human Research

#### Visit 1

Blood test – GFR measurement to be done to evaluate renal insufficiency, liver serum markers, and pregnancy if applicable will be done for research - takes about 10 minutes. DW-MRI and DCE-MRI (MRI with intravenous contrast only if GFR>30) is standard of care and added MRE which is research will be 5 extra minutes (the entire MRI will take about 45 minutes)

Fibroscan and/or ARFI to determine liver stiffness will be done for research - takes about 10-20 minutes.

Visit 1 should take about 60-90 minutes.

Patients under medical treatment for portal hypertension or TIPS procedure are considered to be scheduled for visit 1 before they start their portal hypertension treatment or get TIPS placement.

#### Visit 2

DW-MRI and DCE-MRI (MRI with intravenous contrast only if GFR  $> 60$ ) with MRE sequences is done for research and done for reproducibility and will take another 45 minutes to complete to the first 30 subjects. This visit will take place within a week after visit 1.

This visit may have another blood test and another Fibroscan and/or ARFI so the entire visit should take about 60-90 minutes.

	Protocol Title:	Detection of Liver Fibrosis Using IVIM Diffusion and DCE MRI in HCV
	Principal Investigator Name/Contact Info:	[name]
	Primary Contact Name/Contact Info	[name] [contact] [contact]
	Date Revised:	9/16/2016
	Study Number:	GCO09-1187

Patients under medical treatment for portal hypertension or TIPS procedure are considered to be scheduled for visit 2 after they started their portal hypertension treatment or got TIPS placement to look at changes in hepatic flow and liver stiffness.

Patients starting antiviral therapy for HCV will be evaluated before they start the therapy, and will be repeated 3 to 6 months after the end of therapy.

We would like to perform the following sub-studies: All subjects will receive by default Gd-BOPTA (Multihance, Bracco) enhanced MRI (half dose at 0.05 mmol/Kg for the perfusion study) at 1.5T or 3T. In addition, the subjects may receive one of the following options:

**Option 1:** 1.5T MRI using (Gadoxedate disodium (Eovist)) will be performed in up to 10 subjects.

- Sub-arm 1: In up to 5 subjects receiving Gadoxedate disodium (Eovist), the studies will be repeated twice at least 24h apart to measure reproducibility of DCE-MRI using Gadoxedate disodium (Eovist)

**Option 2:** 3T MRI using Gd-BOPTA (same dose as above), will be performed in up to 10 subjects. These could be different or same subjects as in option 1.

MR Elastography: Will be performed in all patients before contrast injection, using a 1.5 and/or 3T system (Siemens). The patient will be asked to perform multiple breath-holds during the image acquisition.

**Option 3:** Compare image quality and liver perfusion quantification between Cartesian and radial DCE-MRI acquisitions in a small subset of subjects (n=15), using the same contrast dose and MR system.

The liver explant analysis will be performed as part of routine clinical care. In addition, the following will be assessed: degree of biliary differentiation (by measuring semiquantitatively cytokeratin-19 expression).

Extra MRI sequences of the abdomen will be done for research.

Fibroscan and/or ARFI to determine liver stiffness will be done for research.

A blood test will be done to evaluate renal insufficiency, only if no recent EGFR value (not older than 6 weeks) is available in the medical record for contrast administration determination.

A blood test will be done to evaluate liver serum markers for research purposes.

A pregnancy test, if pregnancy cannot be excluded by women of child-bearing potential, will be performed prior to any scan to determine eligibility for study participation.

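### Sections 5(b) and 5(f) give opposite answers on gadolinium contrast at a GFR of exactly 30 (first scan) and exactly 60 (repeat scan)

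*Combined protocol and SAP*

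**What the plan says.** Section 5(b), under Exclusion criteria, sets the limits by GFR band:

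- Lower limit: "Subjects with GFR <30 will not undergo DCE-MRI with Gadolinium contrast". These subjects may still be enrolled for a non-contrast protocol.
- Middle band: the sentence opening "Subjects with GFR between 30 and" continues "60 will receive only either a half dose Multihance or Gadoxedate disodium (Eovist", and rules out repeat contrast studies for this band.
- Upper limit: only subjects at 60 or above "will be proposed to return for repeat DCE-MRI studies with Gadolinium contrast". Those below 60 may be considered for non-contrast repeats.

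Section 5(f), Procedures Involved in the Human Research, restates the limits by visit:

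- Visit 1: "MRI with intravenous contrast only if GFR>30".
- Visit 2: the same form of words, with the limit above 60.

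Section 5(f) also speaks twice about where the GFR comes from. Visit 1 lists a "GFR measurement to be done to evaluate renal insufficiency". Later in the section, the renal blood test is done "only if no recent EGFR value (not older than 6 weeks) is available in the medical record".

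**The concern.** A contrast limit is a decision rule, so staff need one answer for every possible value. Here the answer at each limit depends on which section is open. Someone working from section 5(b) could give contrast that section 5(f) forbids, and someone working from section 5(f) could withhold contrast that section 5(b) permits. Either could be recorded as a deviation.

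Two things depend on the rule. The first is exposure: section 6 links gadolinium in severe kidney disease to nephrogenic systemic fibrosis, which it calls very rare but serious and sometimes deadly. Section 5(i) gives safety monitoring as not applicable because the risk is minimal, so the written limit carries much of the protection. The second is data: the rule settles who contributes a DCE-MRI measurement and who contributes a repeat one for reproducibility.

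**Working it through.** The plan gives no figure to reproduce. The check codes each rule as a condition on GFR, written g, and compares the two sections.

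**Inputs**

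- First contrast, section 5(b): not barred if NOT (g < 30), that is, g ≥ 30.
- First contrast, section 5(f) Visit 1: allowed only if g > 30.
- Repeat contrast, section 5(b): allowed if g ≥ 60.
- Repeat contrast, section 5(f) Visit 2: allowed only if g > 60.

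**Results around the limits**

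| GFR | First contrast, 5(b) | First contrast, 5(f) Visit 1 | Repeat contrast, 5(b) | Repeat contrast, 5(f) Visit 2 |
|---|---|---|---|---|
| 29 | barred | barred | barred | barred |
| **30** | **not barred** | **barred** | barred | barred |
| 31 | not barred | allowed | barred | barred |
| 59 | not barred | allowed | barred | barred |
| **60** | not barred | allowed | **allowed** | **barred** |
| 61 | not barred | allowed | allowed | allowed |

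Across the 131 whole numbers from 0 to 130, the first-contrast rules differ only at 30 and the repeat-contrast rules only at 60.

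**How many subjects.** The count would be the number of subjects eligible for a first contrast scan whose GFR is exactly 30, plus the number considered for a repeat contrast scan whose GFR is exactly 60. The documents give no GFR distribution and do not say how GFR is rounded, so neither number can be derived. The planned total of 250 in section 5(c) is not the base for the limit at 60, because that limit concerns repeat contrast only. The Visit 2 reproducibility scan is planned for the first 30 subjects. The sub-studies are capped at 10 (Option 1) and 10 (Option 2), with 15 in Option 3, and the treatment-follow-up groups have no stated size.

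**GFR source.** Section 5(b) is silent on which GFR value counts, so this question lies within section 5(f). The Visit 1 text is unconditional and the later text is conditional. The choice between a chart value and a same-visit value changes a decision only when the two fall on opposite sides of 30 or 60. At Visit 2 another blood test is optional, and the text for that visit does not name the value that governs repeat contrast.

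**The case against.** The strongest reply is that this is an editorial slip: two one-point mismatches that few subjects will ever meet. That is right about reach. The risk text also limits the harm argument. It ties nephrogenic systemic fibrosis to severe kidney disease and says the condition has not been seen with normal function or mild problems, so it bears more clearly on the limit at 30 than on the one at 60. Nor does a subject lose a place in the study, since section 5(b) keeps a non-contrast route open. None of this supplies a single answer at 30 or at 60.

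A reader might infer three wider faults, which the documents do not support:

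- *That 60 also sits in section 5(b)'s restricted band, so that section 5(b) contradicts itself.* The wording of the band leaves its endpoints open, but the next sentences assign repeat contrast to 60 and above and non-contrast repeats to values below 60. Read together, they place 60 outside the no-repeat group.
- *That the half-dose restriction is empty, because section 5(f) gives every subject* "half dose at 0.05 mmol/Kg for the perfusion study" *by default.* Section 5(b) limits the middle band to one agent or the other and rules out repeat contrast, whereas section 5(f) lets other subjects have an optional further study in addition to the default. The restriction therefore has content despite the shared dose label.
- *That the two GFR-source statements are a full contradiction touching everyone with a recent chart value.* The later sentence reads naturally as the specific condition on the general Visit 1 statement, and it ties the chart value to the contrast decision. A cross-reference is enough.

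**Conclusion.** The point holds as a narrow inconsistency in the current text. At a GFR of exactly 30, section 5(b) does not bar contrast and section 5(f) Visit 1 does. At exactly 60, section 5(b) allows repeat contrast and section 5(f) Visit 2 does not. At every other value the two sections agree.

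The conclusion rests only on reading the four inequalities literally and needs no distributional assumption. A reader might want to attach a count, for example by spreading GFR evenly over some range and applying it to all 250 subjects. Nothing in the documents supports such a spread, so the size can be stated only as few. A material effect on the DCE results has not been shown either. The case for acting is that the rule governs exposure to a contrast agent and is very cheap to correct. The documents do not show which version was intended, and this review does not prefer one.

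**What to change.** 1. Reconcile the Exclusion criteria in section 5(b) with the Visit 1 and Visit 2 text in section 5(f), so that each limit has one inequality. The responsible clinicians decide which version stands. Both sections should then use identical wording, or one should cite the other.
2. As a secondary clarification within section 5(f), make the Visit 1 statement on GFR measurement refer to the later six-week chart-value condition. State for each visit, including Visit 2, which GFR value governs contrast.

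The cost is a short amendment of a few sentences. Sample size, procedures and analysis are unchanged. If subjects have already been scanned, a check of records for GFR values of exactly 30 at a first contrast decision or exactly 60 at a repeat one would show whether the discrepancy ever mattered.
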